8.4 Exploratory Efficacy Endpoints

The exploratory efficacy endpoints are listed below. The exploratory efficacy endpoints, when applicable, will be evaluated at a nominal 0.05 level (2-sided) without adjusting for multiplicity.

SAP 405-201-00014

- 1) Change from baseline for Question 1 (Global Quality of Life) and Questions 9Aa – 9Ai and 9Ba – 9Bi (Impact of Symptoms) of AIM-A at scheduled visits during the double-blind treatment period, separately at every visit
- 2) Proportion of subjects in each response for the following questions of AIM-A at scheduled visits during the double-blind treatment period, separately at every visit
 - a. Questions 2-4 (Global Quality of Life)
 - b. Questions 5a-5j (Living with ADHD)
 - c. Questions 6a-6k (General Well-Being)
 - d. Questions 7a-7j (Work, Home and School Performance and Daily Functioning)
 - e. Questions 8a-8h (Relationships and Communication)
 - f. Economic impact (5 items)
 - g. Questions 17-23 (Demographics/Medication Status)
- 3) Change from baseline in the total score of (18 item) ADHD Symptoms score of the ASRS and subscale scores for ASRS at scheduled visits during the double-blind treatment period, separately at every visit

Variables (1) and (3) will be evaluated using the same MMRM model described in the primary analysis. Variable (2) will be summarized by descriptive statistics and no statistical comparisons between centanafadine and placebo will be performed.

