3.5.3 Exploratory Endpoints

The exploratory endpoints are the change from baseline to Day 28 and Day 42 in the ADHD Impact Module - Adult (AIM-A) and the Adult ADHD Self Report Scale (ASRS) total score and subscale scores.

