3.7.3.3 Attention-deficit/Hyperactivity Disorder Impact Module - Adult

The AIM-A (Table 3.7-1) is a subject self-report questionnaire which assesses quality of life in adults with ADHD. The questionnaire has 4 global quality of life items, 5 economic impact items, and 5 multi-item scales that assess the following key concepts: Living with ADHD, General Well-Being, Work, Home and School Performance and Daily Functioning. Additionally, Relationships and Communication, and Impact of Symptoms are also included.³⁴

Protocol 405-201-00014

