3.7.3.4 Adult Attention-deficit/Hyperactivity Disorder Self-Report Scale, Expanded Version

The ASRS Version 1.1, ([Table 3.7-1](#)) is a self-report questionnaire developed by the WHO. The subject will answer 31 questions. Of those 31, 18 of the questions pertain to the 18 DSM-5 ADHD symptoms (ADHD Symptoms). The expanded version includes 9 additional items that assess Executive Function Deficits, and 4 items that assess Emotional Dyscontrol.³⁵

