7.3.3 Exploratory Efficacy Endpoint Analyses

Statistical analysis of the exploratory endpoints will be further described in the SAP.

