10.3.4 Attention-Deficit Hyperactivity Disorder Impact Module – Adult (AIM-A)

The AIM-A is a subject self-report questionnaire which assesses quality of life in adults with ADHD. The questionnaire has 4 global quality of life items, 5 economic impact items, and

SAP 405-201-00014

5 multi-item scales that assess the following key concepts: Living with ADHD, General Well-Being, Work, Home and School Performance and Daily Functioning. Additionally, Relationships and Communication, and Impact of Symptoms are also included.

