10.3.5 Adult ADHD Self Report Scale (ASRS)

The ASRS is a self-report questionnaire developed by the WHO. The subject will answer 18 questions about the frequency of recent ADHD symptoms that are consistent with the DSM-IV criteria. The ASRS is assessed at the scheduled visits during the screening period, the single-blind placebo run-in period, and at Days -1, 28 and 42/ET during the double-blind treatment period.

The total score of (18 item) ADHD Symptoms score of the ASRS is set to be missing if more than one item of a subscale is missing for inattentive subscale or hyperactive-impulsive subscale, separately. If one item is missing for a given subscale (inattentive or hyperactive-impulsive), then the subscale score is derived as the mean of scores from the 8 non-missing items multiplied by 9. All imputed scores are rounded to the first decimal place. The 9 inattentive items consist of items 1-4 and 7-11 and the 9 hyperactive impulsive items consist of items 5-6 and 12-18.

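### SAP 8.4 analyses the protocol's exploratory AIM-A and ASRS endpoints only in part: four of five AIM-A scales have no change score or placebo comparison, and 13 of the protocol's 31 ASRS items have no named analysis

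*SAP*

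**What the plan says.** Protocol 3.5.3 fixes the variable and the time points: "The exploratory endpoints are the change from baseline to Day 28 and Day 42 in the ADHD Impact Module - Adult (AIM-A"), and in the same sentence "the Adult ADHD Self Report Scale (ASRS) total score and subscale scores". Protocol 7.3.3 leaves the method open: "Statistical analysis of the exploratory endpoints will be further described in the SAP".

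On the AIM-A, Protocol 3.7.3.3 states that "The questionnaire has 4 global quality of life items, 5 economic impact items, and 5 multi-item scales", and SAP 10.3.4 repeats this structure. SAP 8.4 then divides the instrument:

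- Variable (1): change from baseline for Question 1 and for the Impact of Symptoms questions, by the primary-analysis MMRM.
- Variable (2): the share of subjects choosing each response, for Questions 2-4, the four remaining multi-item scales (Questions 5 to 8), the economic items and Questions 17-23. For these, "Variable (2) will be summarized by descriptive statistics and no statistical comparisons between centanafadine and placebo will be performed".

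On the ASRS, Protocol 3.7.3.4 has subjects answer 31 questions, 18 of them on DSM-5 symptoms; "The expanded version includes 9 additional items that assess Executive Function Deficits, and 4 items that assess Emotional Dyscontrol". SAP 10.3.5 says "The subject will answer 18 questions about the frequency of recent ADHD symptoms" and defines two subscales, inattentive and hyperactive-impulsive. Variable (3) of SAP 8.4 is change in the 18-item total and in unnamed subscale scores, by the same MMRM.

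**The concern.** The protocol delegates the method for the exploratory endpoints, not the variable. For four of the five AIM-A scales the SAP replaces a change from baseline with a distribution of responses at each visit, and rules out any comparison with placebo. It gives no reason for treating Questions 5 to 8 differently from Question 9. Followed exactly, the SAP would not deliver that part of the stated endpoint.

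The AIM-A is the only quality-of-life questionnaire in the assessment schedule. Four of its five scale domains would yield no effect estimate. The same would hold for executive function and emotional dyscontrol on the ASRS, if those items were on the form used.

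**Working it through.** No formula is involved. The check is a count and a matching of sections.

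**AIM-A.** Inputs: the five scales in Protocol 3.7.3.3 and the question ranges in SAP 8.4.

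| Scale | Questions | Number | SAP treatment |
|---|---|---|---|
| Living with ADHD | 5a-5j | 10 | proportions, no comparison |
| General Well-Being | 6a-6k | 11 | proportions, no comparison |
| Performance and daily functioning | 7a-7j | 10 | proportions, no comparison |
| Relationships and Communication | 8a-8h | 8 | proportions, no comparison |
| Impact of Symptoms | 9Aa-9Ai, 9Ba-9Bi | 9 + 9 = 18 | change from baseline, MMRM |

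Scales without a change analysis: 4 of 5. Questions in them: 10 + 11 + 10 + 8 = 39.

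Timing does not explain the split. Protocol Table 3.7-1 schedules the whole AIM-A at baseline, Day 28 and Day 42/ET. Scoring may explain it: SAP 10.3.4 has no scoring or missing-item rule for any AIM-A scale, whereas 10.3.1 and 10.3.5 give both for the AISRS and the 18-item ASRS. Tables CT-5.7.1 to CT-5.7.4 promise mean change on the AIM-A without defining a score. CT-5.7.5 is the single table for the proportions.

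**ASRS.** The protocol's own figure reproduces: 18 + 9 + 4 = 31. Items outside the 18: 31 - 18 = 13, and 13/31 = 42%.

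Three places in the SAP document could have covered those 13 items:

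1. Scoring rules (10.3.5): items 1-18 only, in two subscales of 9.
2. Table list (section 13): CT-5.8.x for the scale and CT-5.9.x for the two symptom subscales; nothing for executive function or emotional dyscontrol.
3. Line-item analysis (8.5): the output STAT-1.2 in the attached statistical documentation lists 18 items and an 18-item total.

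None of the three names the 13 items.

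**Size of a full analysis.** New scores: 4 AIM-A + 2 ASRS = 6. Comparisons: 6 scores × 2 doses × 2 visits = 24.

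**The case against.** The strongest case against is this. The endpoints are exploratory, tested at a nominal level and outside the fixed sequence. The protocol hands their analysis to the SAP, and describing some items without testing them is a legitimate choice. No section promises a between-group test for every AIM-A scale. In Protocol 3.5.3 the words on total and subscale scores may attach only to the ASRS. Protocol 3.7.3.4 never calls executive function and emotional dyscontrol subscales, while the unnamed subscale scores in SAP 8.4 and the line items in 8.5 are not limited in wording to 18 items. Adding scores adds unadjusted p-values where variable (2) produces none. Neither document gives AIM-A item direction, coding or scoring, so an improvised sum could depart from the instrument.

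Much of this stands. It keeps the point away from the trial's main conclusions, rules out an invented AIM-A score and requires the extra comparisons to be labelled. It does not remove the mismatch. However the 3.5.3 sentence is parsed, change from baseline applies to the AIM-A, and a response proportion is not that. The broad ASRS wording is narrowed by the scoring section, the table list and the output, so no named analysis is a fair description; a flat statement that the SAP forbids one would not be.

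Listing Questions 17-23, which the SAP itself labels as demographics and medication status, under efficacy is housekeeping only.

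**Conclusion.** The point holds as a partial shortfall: 4 of 5 AIM-A scales (39 questions) lack the change from baseline that the protocol specifies and any placebo comparison, and 13 of the 31 ASRS items in the protocol have no named analysis. It should be put right, but it touches neither alpha, power nor the primary and key secondary conclusions.

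Three stronger inferences are not supported:

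- *That the SAP leaves the exploratory endpoints unanalysed.* Question 1, Impact of Symptoms, the 18-item ASRS total and two ASRS subscales are all compared with placebo by MMRM.
- *That the trial can say nothing about quality of life.* Question 1 is the SAP's global quality-of-life item and is compared; what is missing is the other four domains.
- *That all 31 ASRS items were completed by every subject, so that 18 is simply a SAP error.* The documents disagree and do not show which form was used. STAT-1.2 has 124 + 114 + 130 = 368 subjects, against 421 in the Efficacy Sample.

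The AIM-A count assumes that the question ranges in SAP 8.4 are complete. The ASRS count assumes that the protocol's 31-item form was administered.

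**What to change.** 1. In SAP 10.3.4, state the AIM-A multi-item scale scores and missing-item rule from the instrument's own published scoring, with the source cited. Do not construct a sum.
2. In SAP 8.4, analyse change at Days 28 and 42 in those scores with the planned MMRM at the nominal level. If description only is preferred for Questions 5 to 8, declare it as a departure from Protocol 3.5.3 and give the reason.
3. Check the ASRS form actually used and make Protocol 3.7.3.4 and SAP 10.3.5 agree. If 31 items were collected, define Executive Function and Emotional Dyscontrol scores, add them to the same model and name all ASRS subscales in 8.4. If 18 were collected, say so.
4. Move Questions 17-23 to the baseline and medication summaries.

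The cost is SAP text, a few tables and up to about 24 extra unadjusted comparisons, fewer if the two ASRS scores do not apply. The AIM-A data are already in the visit schedule. The comparisons should be labelled exploratory, or post hoc if added after unblinding; the statistical documentation attached to the SAP already holds treatment-group results run on 31 August 2020.

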8.5 Exploratory Analysis

Exploratory efficacy analyses will be presented in Statistical Documentation.

Treatment-by-center interaction will be assessed at Day 42 by including the treatment-by-center-by-visit interaction in the model. Results for study centers will be displayed from largest center to smallest center.

Line Item score will be performed for AISRS and ASRS on Change from baseline of the double-blind treatment period to Day 42 using the MMRM model for AISRS and ASRS, where Cohen's D Effect Size¹⁰ is the difference between the two means divided by their standard deviation [as defined by Cohen's D and reviewed on pages 4-6 from the Sage book "Effect Size for ANOVA Designs" (Vol 129) by Cortina and Nouri]. For MMRM (using SAS PROC MIXED), or ANCOVA (Using SAS PROC GLM), LSMean difference of treatment effects for the between centanafadine and placebo groups, and the standard error of the difference (Stderr) will be obtained with an Estimate statement. Let n_1 and n_2 denote the

SAP 405-201-00014

respective sample sizes of the two groups to compare, Effect Size = $d = (\text{LSMean}_1 - \text{LSMean}_2) / \sigma$, where $\sigma = \frac{\text{Stderr}}{\sqrt{\frac{1}{n_1} + \frac{1}{n_2}}}$.

9 Safety Analysis

Standard safety variables to be analyzed include AEs, clinical laboratory tests, vital signs, electrocardiograms (ECGs), body weight, waist circumference, and BMI. In addition, data from the following safety scales will be evaluated: C-SSRS and Study Medication Withdrawal Questionnaire (SMWQ).

Analyses of the double-blind treatment period safety data will be performed on the Safety Sample unless indicated otherwise.

The Safety Sample will also be analyzed for the single-blind placebo lead-in period safety data, as applicable, by treatment groups the subjects eventually being assigned in the double-blind treatment period.

9.1 Adverse Events

All adverse events (AEs) will be coded by system organ class (SOC) and Medical Dictionary for Regulatory Activities (MedDRA) Preferred Term (PT). The incidence of the following events will be summarized:

- a) Treatment-emergent AEs (TEAEs)
- b) TEAEs by severity
- c) TEAEs potentially causally related to the IMP
- d) TEAEs with an outcome of death
- e) Serious TEAEs
- f) TEAEs leading to discontinuation of the IMP
- g) Treatment-emergent Adverse Events of Special Interest (AESI)
- h) Abuse-related TEAEs and TEAEs involving MHIs (Medication handling irregularities)

AEs will be classified by Primary SOC and PT according to the MedDRA. AEs that are gender-specific, e.g., ovarian cancer, will have their incidence rates evaluated for the specific gender.

Incidence of TEAEs will be summarized by double-blind treatment group for the double-blind treatment period. Incidence of TEAEs by SOC and MedDRA PT will be summarized for sex and race.

SAP 405-201-00014

Adverse Events of Special Interest

Newly acquired skin eruptions that are non-traumatic will be considered AESIs. These may include but are not limited to eruptions such as skin rashes, skin irritations, skin reactions, or acneiform lesions. This does not include localized contact irritation at ECG lead sites due to application or removal of lead adhesive.

Refer to the separate rash workup plan for complete details, including reporting forms, and extra measures that must be performed to characterize any skin AESI of a newly acquired skin eruption that is non-traumatic. The trial site will have a local designated dermatologist available for immediate consultation during the trial for these AESIs.

9.1.1 Adverse Events in the Double-Blind Treatment Period

TEAEs in the double-blind treatment period are defined as AEs with an onset date on or after the start of double-blind treatment. In more detail, TEAEs are all adverse events which started after start of double-blind IMP; or if the event was continuous from end of the single-blind placebo run-in period and was worsening, serious, study drug related, or resulted in death, discontinuation, interruption or reduction of study therapy. Adverse Events occurring up to 30 days after the last day of double-blind dosing will be included in the summary tables.

The incidence of AEs in the double-blind treatment period will be tabulated by treatment group and overall using the Safety Sample. Incidence of TEAE during the double-blind treatment period of at least 5% in either centanafadine group and also greater than placebo by SOC and MedDRA PT will be provided.

Unless otherwise specified, in general, analysis of safety data will be performed on observed case and for last visit.

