3.9 Screen Failures

A screen failure subject is one from whom informed consent is obtained and is documented in writing (ie, subject signs an eICF), but who is not randomized or assigned to trial treatment.

For this trial, treatment begins with the first dose of the IMP in the single-blind placebo run-in period. Subjects that have a positive alcohol test (via breathalyzer or blood), or positive drug screen for cocaine, or other illicit drugs (excluding marijuana) are not eligible to be retested or rescreened, and will be considered screen failures. Subjects that test positive for marijuana may be permitted to be enrolled if they have no evidence of a substance use disorder, and if they agree to refrain from use for the duration of the trial. Allowance for subjects testing positive for marijuana at screening require explicit approval from the medical monitor. Subjects that test positive for confirmed prescription use of ADHD medications at screening will be required to undergo a washout period (Section 4.1). If after the allotted washout period, a subject tests positive for ADHD medications prior to the start of the single blind placebo run-in period, subjects will be screen failed, and not permitted to rescreen. Screen failures previously excluded for a positive urine drug screen due to use of prescription or over-the-counter (OTC) medications or products not used for the treatment of ADHD, may be retested or rescreened for participation in the trial only with the explicit consent of the medical monitor. Subjects will be administered the ASRS prior to the start of the single-blind placebo run-in period, and those with a $\geq 30\%$ improvement in the (18-item) ADHD Symptoms score compared to the score at screening will be screen failed, and not eligible for rescreening. Screen failures excluded for any other reasons may be rescreened at any time if the exclusion characteristic has changed. In the event that a screen failure is rescreened a new eICF must be signed, a new screening number assigned, and all screening procedures repeated.

Protocol 405-201-00014

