9.1.2 Adverse Events in the Single-blind Placebo Run-in Period

Adverse Events in the single-blind placebo run-in period will be summarized for patients in the Safety Sample. AEs occurring up to 30 days after the last day of IMP in this period, but prior to the start of the double-blind treatment period, will be included in these summary tables. The incidence of adverse events in the single-blind placebo run-in period will be tabulated by the double-blind treatment patients receive in the double-blind treatment period.

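### SAP 9.1.1 gives two TEAE definitions that disagree; read literally, the second admits run-in events that were serious or drug related with no change after the first double-blind dose

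*SAP*

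**What the plan says.** SAP 9.1.1 opens with an onset rule: "TEAEs in the double-blind treatment period are defined as AEs with an onset date on or after the start of double-blind treatment". The next sentence, offered as more detail, keeps that rule but adds a second route. An event also counts "if the event was continuous from end of the single-blind placebo run-in period and was worsening, serious, study drug related, or resulted in death", or if it led to discontinuation, interruption or reduction of study therapy.

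Four other places bear on how this works:

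- Protocol 3.9 says that "treatment begins with the first dose of the IMP in the single-blind placebo run-in period". Protocol 5.1 has investigators rate causality as related or not related to the IMP.
- SAP 9.1 says "Incidence of TEAEs will be summarized by double-blind treatment group for the double-blind treatment period". The table list in SAP 13 includes potentially drug-related TEAEs by arm (CT-8.3.1).
- SAP 9.1.1 calls for a common-event table: "Incidence of TEAE during the double-blind treatment period of at least 5% in either centanafadine group and also greater than placebo". SAP 13 adds a 2% version (CT-8.2.1.7).
- SAP 9.1.2 says "Adverse Events in the single-blind placebo run-in period will be summarized for patients in the Safety Sample", tabulated by the arm the subject later receives.

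Protocol 7.5.1 lists TEAE tables but does not define the term, so it does not settle which sentence governs.

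**The concern.** The two sentences classify some events differently. Take a headache that starts in the run-in, is rated related to IMP, and continues at the same grade into Week 1. Under the first sentence it is not a TEAE. Under the second, read literally, it is one, and a drug-related one, in whichever arm the subject is randomized to.

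That event began before randomization, on placebo, so it cannot have been started by the randomized treatment. The trial's blinding makes such records possible: Protocol 3.7.1.2 requires subjects to believe that randomized treatment starts at Visit 2, so complaints attributed to study drug during the run-in are plausible. At stake are the arm incidences, the drug-related and serious TEAE tables, and the choice of terms listed as common.

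**Working it through.** **Reading the rule.** The qualifiers in the second sentence are alternatives, so worsening is sufficient but not necessary. Worsening describes a change. Serious and drug related are fields on an AE record and carry no date in this sentence. A programmer could flag a continuing run-in record on either field alone. Such a record would then be counted under both 9.1.1 and 9.1.2.

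**Size.** The documents give no run-in AE rate, carry-in rate or expected TEAE incidence, so there is no stated figure to reproduce. All event rates below are assumptions. The planned arm size, 150, is from SAP 4.

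Let *c* be the share of each arm carrying in one preferred term unchanged, equal across arms in expectation because the events precede randomization. Let *p* be the true double-blind incidence, with carry-in independent of a later event of that term. Then:

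- reported incidence = c + (1 − c)p
- reported risk difference = (1 − c) × true risk difference
- reported risk ratio = [c + (1 − c)p_drug] / [c + (1 − c)p_placebo]

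For an assumed 10% on drug and 5% on placebo, at c = 1%: placebo 0.01 + 0.99 × 0.05 = 5.95%; drug 0.01 + 0.99 × 0.10 = 10.90%.

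| c | Subjects per arm (150c) | Placebo | Drug | Risk difference | Risk ratio |
|---|---|---|---|---|---|
| 0 | 0 | 5.00% | 10.00% | 5.00 points | 2.00 |
| 0.5% | 0.75 | 5.48% | 10.45% | 4.98 points | 1.91 |
| 1% | 1.5 | 5.95% | 10.90% | 4.95 points | 1.83 |
| 3% | 4.5 | 7.85% | 12.70% | 4.85 points | 1.62 |

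The 3% row is a stress case. It needs 4 or 5 subjects per arm with the same term, begun within one week of placebo, still present at the first double-blind dose, unchanged, and serious or rated related.

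**Display thresholds.** With 150 per arm, 5% is 7.5 subjects, so 8 are needed; 2% is 3 subjects. Let m be that minimum, X_p and X_d the binomial counts on placebo and on one centanafadine arm, and both centanafadine arms have the same incidence. The chance that at least one of them reaches m and exceeds placebo is

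Σ_k P(X_p = k) × {1 − [1 − P(X_d ≥ max(m, k + 1))]²}.

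| Rule | Assumed true incidence, drug / placebo | c = 0 | c = 0.5% | c = 1% |
|---|---|---|---|---|
| 5% | 3% / 3% (no effect) | 15% | 26% | 37% |
| 5% | 4.5% / 2% | 59% | 71% | 80% |
| 5% | 10% / 5% | 99% | 98% | 98% |
| 2% | 1% / 1% (no effect) | 30% | 47% | 55% |

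Terms near a threshold are sensitive to even one or two carried-in subjects per arm. Terms well above it are not.

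**The case against.** **The sentence can be read sensibly.** For a subject who was randomized and dosed, an event that resulted in death or discontinuation must have done so after double-blind dosing began, and worsening naturally means worsening after that point. Serious and drug related can then be taken as status during double-blind treatment. This stands in part: the literal reading is not the only one, and a reader who infers that the SAP certainly counts unchanged events goes further than the text. But the SAP does not state the timing, and the first sentence still excludes every event with earlier onset. The sentence needs editing on either reading.

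**The affected set is probably small.** The run-in lasts one week. It is single-blind, and sites dispense a known placebo, so they have less reason to rate an event related. Subjects who stop in the run-in never reach the Safety Sample. Medical history and eligibility are reviewed again at baseline, so an ongoing serious event at randomization should be rare. This stands, and it limits the size of the point.

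**No planned comparison is harmed.** The SAP plans descriptive AE incidence, with no AE risk ratio or significance test. A reader might infer that drug–placebo contrasts are materially diluted. The documents do not support that: the risk difference only scales by 1 − c. The risk ratio moves more, but it is not a planned statistic and its movement depends wholly on assumed rates.

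**Extra terms are conservative, and the run-in tables show the background.** Crossing a threshold does list more terms rather than fewer. It also attributes pre-randomization events to randomized treatment, which matters most in the drug-related table. The run-in tables show all run-in events, and no table in SAP 13 identifies those also counted in the double-blind period, so a reader cannot subtract them.

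**Conclusion.** The inconsistency is real, and the documents do not resolve it. It is a fault of definition and attribution, not a demonstrated bias. With equal carry-in across arms, 1% for one term would change a 5.00-point risk difference to 4.95, while adding nearly 1 percentage point to each arm's incidence (5.00% to 5.95% and 10.00% to 10.90%). The clearest numerical effect is on which near-threshold terms appear in the 5% and 2% tables. These figures rest on assumed incidences and carry-in rates; the true carry-in rate is unknown and probably below the higher values shown. The drug-relatedness qualifier is the main exposure, because unchanged serious run-in events should be rare.

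**What to change.** Replace the two sentences in SAP 9.1.1 with one definition. A double-blind TEAE is an AE with onset on or after the first double-blind dose, or a run-in AE that, **after that dose**, worsens, becomes serious, becomes related to double-blind IMP, or results in death, discontinuation, interruption or reduction of study therapy. This keeps every qualifier now listed, including interruption and reduction, and gives each the same time anchor. Run-in events that continue unchanged are reported only in the run-in tables of 9.1.2.

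The cost is one SAP sentence, one flag in the AE dataset and slightly smaller TEAE counts. Applying the flag needs the date on which a continuing event changed status; where the record lacks that date, the SAP should say how the event is handled. If AE tables have already been produced, re-flag, state how many events move in each arm, and document the change.
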